## 10 STUDY VISIT SCHEDULE

Subjects will be assigned to one of two arms in the study: a regular absorbency arm or a super absorbency arm. Within each arm, a subset of 60 subjects (Subset Population) will undergo gynecological exams prior to and following tampon use. The study visit schedule is the same for both arms of the study.

For subjects in the Subset Population, the study will consist of 4 visits for each study subject, 2 visits for each menstrual cycle: one before and after each menstrual cycle.

For all other subjects, the study will consist of 3 visits: a screening and pre-use visit, and two post-use visits.

Pre-use visits will be conducted within 72 hours prior to expected menstruation. Post-use visits are to be completed within 72 hours following the last tampon use for that menstrual cycle.

The schedule of visits and timing of procedures are summarized in the Proposed Schedule of Events (Table 1 - Proposed Schedule of Events).

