#### **Recording Adverse Events**

Adverse events spontaneously reported by the subject and/or in response to an open question from the study personnel or revealed by observation will be recorded during the study at the investigational site. Information about AEs will be collected from the Test Article Dispensation until the end of the study. Serious Adverse Event information will be collected from Test Article Dispensation until 7 days following Visit 4 (Post-use Visit). The AE term should be reported in standard medical terminology when possible. For each AE, the investigator will evaluate and report the onset (date and time), resolution (date and time), intensity, frequency, relationship to test article, action taken, serious outcome (if applicable), and whether or not it caused the subject to discontinue the study.

Intensity will be assessed according to the following scale:

- Mild (awareness of sign or symptom, but easily tolerated)
- Moderate (discomfort sufficient to cause interference with normal activities)
- Severe (incapacitating, with inability to perform normal activities)

It is important to distinguish between serious and severe AEs. An AE of severe intensity may not be considered serious.

Relationship to test article will be assessed according to the following scale:

- Not Related - A clearly evident relationship to other etiologies exists and/or the event is not temporally consistent with test article use.
- Unlikely - Based upon available information, a causal relationship to test article is improbable. Usually, another cause is most plausible.
- Possible - Event follows a reasonable temporal association with test article use and is clinically/biological plausible. Other etiologies are also possible.
- Probable - A reasonable temporal sequence of the event with test article use exists and based upon the medical professional's clinical experience, the association of the event with test article seems very likely.

- Definite - Event is clearly related to article use. It is temporally associated with test article use, follows a known or expected response pattern, and improves when stopping test. Other causes do not appear to explain the event.

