If partial adverse event onset times occur, the convention is as follows: if the missing time occurs on the day of the first test article insertion and both the hour and minute are missing then the time assigned is the time of the first test article insertion, otherwise if both the hour and minute are missing and the date is not the date of first test article insertion the time assigned is 12:00; if the date is the same as the date of the first test article insertion and only hour is missing the hour assigned is 12 or the hour of first test article insertion, whichever is later, and if the date is the same as the date of first test article insertion and only the minute is missing the minute assigned is 30 or the minute of first test article insertion, whichever is later. Otherwise the hour assigned is 12 if the hour is missing and the date is not the same as the date of first test article insertion and the minute assigned is 30 if the the date is not the same as the date of first test article insertion.

The following precaution will be considered when applying these conventions to adverse event onset dates and times: if the missing date and time reflect the date and time of onset of an adverse event, the modified date and time will be constructed to match the first documented date/time post test article administration while preserving the order in which the adverse event (AE) was reported in the CRF.

7. Study Subjects and Demographics

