9.1. Adverse Events

All AEs and serious adverse events (SAEs) will be coded using the MedDRA v. 25.1.

All AE data will be summarized for 3 periods: before any test article use, during and following test tampon use, during and following reference tampon use. AEs will be assigned to an analysis period based on the below criteria. The criteria for assigning AEs to an analysis period will differ depending on the type of test article (reference or test tampon) first used by the subject.

Test article order	Criteria for assigning AEs to analysis periods
Reference tampon → Test tampon	If the start date of the adverse event was before the date of first insertion of a reference tampon, then the AE will be assigned to the “before any test article use” period. If the start date of the adverse event was on or after the date of first insertion of a reference tampon, but before the date of first insertion of a test tampon, then the adverse event will be assigned to the “during and following reference tampon use” period. If the start date of the adverse event was on or after the date of first insertion of a test tampon, then the adverse event will be assigned to the “during and following test tampon use” period.

Test tampon → Reference tampon	
If the start date of the adverse event was before the date of first insertion of a test tampon, then the AE will be assigned to the “before any test article use” period.
 
If the start date of the adverse event was on or after the date of first insertion of a test tampon, but before the date of first insertion of a reference tampon, then the adverse event will be assigned to the “during and following test tampon use” period.
 
If the start date of the adverse event was on or after the date of first insertion of a reference tampon, then the adverse event will be assigned to the “during and following reference tampon use” period.

--------------------------------	--

An overall summary of AEs will be provided; this will present number and percentage of subjects who reported at least 1 of the following: any AE, AEs by maximum severity, AEs by maximum relationship to study product, AEs by maximum frequency, and SAEs.

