Abbreviations: AE = adverse event; SAE = serious adverse event.

Note: Percentages are n/Number of subjects in the Safety Population within absorbency group*100. AEs that began prior to insertion of any test article are summarized under Before Any Test Article Use. For subjects randomized to use the test tampon first, AEs that began on or after the date of insertion of first test tampon and prior to date of insertion of first reference tampon are summarized under During and Following Test Tampon Use, and AEs that began on or after the date of insertion of first reference tampon are summarized under During and Following Reference Tampon Use. For subjects randomized to use the reference tampon first, AEs that began on or after the date of insertion of first reference tampon and prior to date of insertion of first test tampon are summarized under During and Following Reference Tampon Use, and AEs that began on or after the date of insertion of first test tampon are summarized under During and Following Test Tampon Use. N is the number of subjects within each period and within absorbency arm.

[1] Subjects are counted only once at the worst severity. If a severity designation is missing, it will be considered as Severe.

[2] Subjects are counted only once at the strongest possible relationship. If a relationship designation is missing, it will be considered as Definite.

[3] Subjects are counted only once at the highest possible frequency. If a frequency designation is missing, it will be considered as Continuous.

Reference Listing: 16.2.7.1

Programming Note: Repeat for Absorbency Arm: Super.

Table 14.3.1.2
 Adverse Events by System Organ Class and Preferred Term
 Safety Population

Absorbency Arm: Regular		Before Any Test Article Use (N=XX)	During and Following Test Tampon Use (N=XX)	During and Following Reference Tampon Use (N=XX)
System Organ Class	Preferred Term			
Subjects with at least 1 AE		XX (XX.X%)	XX (XX.X%)	XX (XX.X%)
System Organ Class 1		XX (XX.X%)	XX (XX.X%)	XX (XX.X%)
Preferred Term 1		XX (XX.X%)	XX (XX.X%)	XX (XX.X%)
Preferred Term 2		XX (XX.X%)	XX (XX.X%)	XX (XX.X%)
Preferred Term 3		XX (XX.X%)	XX (XX.X%)	XX (XX.X%)
...				
System Organ Class 2		XX (XX.X%)	XX (XX.X%)	XX (XX.X%)
Preferred Term 1		XX (XX.X%)	XX (XX.X%)	XX (XX.X%)
Preferred Term 2		XX (XX.X%)	XX (XX.X%)	XX (XX.X%)
Preferred Term 3		XX (XX.X%)	XX (XX.X%)	XX (XX.X%)
...				

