Subject ID	Study Visit	Date Returned (Study Day)	Diary Number	Tampon Code	Diary Entry for Each Tampon Used?	Are All Diary Entries Accurate and Complete?	Were All Discrepancies Addressed and Corrected with Subject?
XXXXXX	XXXXXXXX	DDMMYYYY (XX)	1	XX	Yes	Yes	No; XXXXXXXXXXXXXXXXX
	XXXXXXXX	DDMMYYYY (XX)	2	XX	No	No	
XXXXXX	XXXXXXXX	DDMMYYYY (XX)	1	XX	Yes	No	Yes
	XXXXXXXX	DDMMYYYY (XX)	2	XX	Yes	Yes	

Abbreviations: BR = regular absorbency test tampon; BS = super absorbency test tampon; CR = regular absorbency reference tampon; CS = super absorbency reference tampon.

Note: Study day is calculated relative to the date of first insertion of study product (either test or reference tampon).

Programming Note: If the response for "Were all discrepancies addressed and corrected with the subject?" is "No", then concatenate the text for "If no, please explain", e.g., "No; XXXXXXXXXXXXXXXXX". Repeat for Absorbency Arm: Regular and Absorbency Arm: Super.

Listing 16.2.6.1
 Tampon Integrity Assessment
 Safety Population

[figure not shown]
Absorbency Arm: XXX										
Subject ID	Study Visit	Assessment Performed?/ Reason Not Performed	Assessment Date (Study Day)	Number of Used Tampons Returned	Number of Unused Tampons Returned	Menstrual Cycle	Tampon Code Returned	Tampon Number	Length of Elongation (mm)	Picture Taken of Elongated [1]? Picture Taken of Tampon?
XXXXXX	XXXXXX	No/ XXXXXXXXXXXX								
XXXXXX	XXXXXX	Yes	DDMMYYYY (XX)	XX	XX	XX	XX	XX	No	Yes
						XX	XX	XX	No	Yes
						XX	XX	XX	Yes	Yes
						XX	XX	XX	XX	No
						XX	XX	XX	XX	XX
						XX	XX	XX	XX	XX
						XX	XX	XX	XX	XX
						XX	XX	XX	XX	XX
					
XXXXXX	Yes		DDMMYYYY (XX)	XX	XX	XX	XX	XX	XX	XX
						XX	XX	XX	XX	XX
					

Abbreviations: BR = regular absorbency test tampon; BS = super absorbency test tampon; CR = regular absorbency reference tampon; CS = super absorbency reference tampon.

Note: Study day is calculated relative to the date of first insertion of study product (either test or reference tampon).

[1] Any used tampon with a measurement of elongation >10 mm was considered elongated.

Programming Note: Repeat for Absorbency Arm: Regular and Absorbency Arm: Super.

[figure not shown]
Listing 16.2.6.2.1
 Individual Tampon Entry Diary Responses
 Safety Population

Absorbency Arm: XXX

Subject ID	Study Visit	Diary Number	Tampon Code	Entry Number	Date/Time (Study Day) Tampon Inserted	Date/Time (Study Day) Tampon Removed	Able to Remove Tampon?	White Area Remaining on Tampon?	Flow When Using Tampon?	Comments

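### SAP 9.1 assigns adverse events to products by calendar date alone, so an event with onset earlier on the day of a product's first insertion is charged to a product not yet in use

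*SAP*

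**What the plan says.** SAP 9.1 defines three AE periods: before any use, test tampon, and reference tampon. In the reference-then-test order, the condition for the test period is: "If the start date of the adverse event was on or after the date of first insertion of a test tampon". The opposite order has the mirror rule, with the product names exchanged. The notes to the AE table shells repeat it; for the test-then-reference order they read: "AEs that began on or after the date of insertion of first reference tampon are summarized under During and Following Reference Tampon Use". The AE listings carry the same note.

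Times exist on both sides. Protocol section 12 (Recording Adverse Events) states: "the investigator will evaluate and report the onset (date and time), resolution (date and time), intensity, frequency". The diary listing, SAP Listing 16.2.6.2.1, has a column "Date/Time (Study Day) Tampon Inserted". SAP 6.1.5 also fills in absent AE onset times. Its rule for an event dated to the day of first insertion reads: "both the hour and minute are missing then the time assigned is the time of the first test article insertion". No rule in 9.1 then uses the time.

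On visit timing, Protocol section 10 states: "Pre-use visits will be conducted within 72 hours prior to expected menstruation". In the exam subset the second product is handed out at Visit 3, not at Visit 2. Protocol section 8 (Exam Procedures) makes lesions, vaginal infections and other abnormal findings after screening AEs.

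**The concern.** Comparing dates treats everything on the first-insertion day as following the insertion. Two kinds of event break that assumption.

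- **Visit 3 findings.** A woman in the subset is examined before she has the second product in hand. If she starts using it later that day, a finding with onset recorded at the exam is reported under a product she had not yet used.
- **Day-1 symptoms.** In either cycle, a symptom that starts in the morning and precedes the first tampon is charged to that tampon. In cycle 1 it leaves the before-use period; in cycle 2 it leaves the first product's period.

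Tolerability is one of the validation criteria and is judged by reviewing AEs together with exam findings (SAP 2.1.1 and 8.4). The exam tables would show a Visit 3 lesion as a pre-use finding, while the AE tables would show the same lesion as occurring during or after use of that product. AE Listing 16.2.7.1 shows start dates without times, so the conflict could not be resolved there.

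**Working it through.** The plan gives no figure on this point, so there is none to reproduce. The check traces the rule and then sizes the problem under stated assumptions.

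**1. Tracing the rule.** Take a lesion with onset recorded at the Visit 3 exam at 10:00 and a first tampon of the second product inserted at 18:00 the same day.

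| Order | Date rule (SAP 9.1) | Date and time |
|---|---|---|
| Reference then test | Test period | Reference period |
| Test then reference | Reference period | Test period |

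The onset date equals the insertion date, so the on-or-after condition is met in both orders although the exam came eight hours earlier. In the second row the event is taken off the test tampon. Had onset been recorded on an earlier day, or had first use been on a later day, both rules would give the first product's period.

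**2. Can Visit 3 fall on the day of first use?** Yes. The visit window runs up to expected menstruation, women need only predict onset to within 72 hours (inclusion criterion 5), and no rule excludes same-day use.

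**3. Same-day share *s*.** Assume visits between 09:00 and 17:00 (mean 13:00), spread evenly over the 72 hours before expected onset, with first insertion at onset.

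- Prediction exact: *s* = (24 − 13)/72 = 11/72 = 15.3%. Simulation also gives 15.3%.
- Prediction error uniform over ±1, ±2 or ±3 days, counting only women whose menses start after the visit: 10.3%, 10.3% and 10.2%.
- Same errors, but menses may already have begun by the visit (8.3%, 16.7% and 25.0% of women), with first insertion then within 4 hours after it: 17.8%, 25.2% and 32.6%. Check for ±3 days: 0.250 + 0.750 × 0.102 = 0.326.

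The range is therefore about 10–33%.

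**4. Women affected.** Let *r* be the share of exam women with a new Visit 3 lesion whose onset is recorded as that day. The documents give no value; assume 5–20%. Expected number per arm = 60 × *s* × *r*.

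- Low: 60 × 0.10 × 0.05 = 0.3
- Middle: 60 × 0.17 × 0.10 = 1.0
- High: 60 × 0.33 × 0.20 = 4.0

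**5. Day-1 symptoms.** This route is open to all 738 women in both cycles. Nothing in the documents supports a rate, so none is calculated.

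**The case against.** The rule is explicit, prespecified and symmetric between orders. Counting same-day events as on-product is a common cautious convention and agrees with how SAP 6.1.5 handles absent times. The exam tables (14.3.6.1.1 and 14.3.6.1.2) are split by pre-use and post-use visit for each tampon type, so a Visit 3 finding remains visible as pre-use. Same-day cases can be traced by combining the exam listing with the diary listing. Tolerability has no AE threshold or test that a few misplaced events could tip, and investigators also judge relatedness partly on timing.

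Most of this stands and limits the point. The caution argument holds only in part: it works in cycle 1, but in cycle 2 charging the second product also clears the first, and in the test-then-reference order the product cleared is the one being validated.

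A reader might infer more than the documents support:

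- *Every AE found at a same-day Visit 3 is misplaced.* No. The rule uses onset date, not detection date; an AE with an earlier recorded onset stays with the first product.
- *The same-day share is the share of women with a misplaced AE.* No. It counts visits and must be multiplied by an AE rate that is not given.
- *The rule favours the test tampon.* No. Order is randomised within each arm, so events can move either way.
- *A new Visit 3 lesion was caused by the first product.* Not shown. These women are also examined at Visit 2, and a lesion first seen at Visit 3 may have arisen well after use ended. Placing it in the first period follows the order of events and makes no causal claim.

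**Conclusion.** The point holds in a limited form. SAP 9.1 misplaces an AE whenever its recorded onset is on the day of a product's first insertion but before that insertion, and the collected times would in most such cases show this. Both dates must coincide for the error to occur. For Visit 3 lesions the expected size is about 0.3 to 4 of 60 exam women per arm. That range rests on the assumed visit hours, even spread of visits, prediction errors, lesion rates of 5–20%, and onset being recorded as the exam day. The day-1 route could apply to any of the 738 women at an unknown rate. The consequences are some blurring of the test-versus-reference AE comparison and AE tables that contradict the exam tables. This does not threaten the study's conclusion, but it is a cheap improvement worth making before the AE tables are run; a later change to outputs behind a validation criterion would be post hoc.

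**What to change.** Amend SAP 9.1, with matching notes in Tables 14.3.1.1–14.3.1.5, 14.3.2.1 and 14.3.3.1 and Listing 16.2.7.1:

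1. Where AE onset time and the time of a product's first insertion are both actually recorded, assign the period by comparing date and time.
2. Treat an AE whose recorded onset is the Visit 3 pre-use exam itself as preceding the second product. Do not override an earlier recorded onset: forcing everything detected at Visit 3 into the first product's period would misplace events that began before any use.
3. Keep the present date rule where either time is missing or imputed, or where the insertion date is derived under SAP 6.1.5. This matters because the 12:00 default there applies on any day other than the first insertion in the study, including the day the second product is started, and comparing against a default would give arbitrary results.
4. Show onset time in the AE listing, so that same-day cases can be checked.

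The cost is SAP wording and a few lines of code, with no new data. The downside is that recorded onset and insertion times may be approximate, so some same-day assignments will remain uncertain.

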9.1.1. Serious Adverse Events

All SAEs that occur during the study will be listed by absorbency arm and also tabulated by system organ class and preferred term and presented by absorbency arm.

9.2. Clinical Laboratory Evaluations

No clinical laboratory evaluations are planned to be collected for this study.

9.3. Vital Signs

No vital signs are planned to be collected for this study.

9.4. Electrocardiograms

No electrocardiograms are planned to be performed for this study.

9.5. Gynecological Examination

A subset of subjects will undergo a gynecological examination at each study visit prior to and following tampon use. Vaginal pH, and the number and percentage of subjects with any lesions, a suspected infection, other abnormal findings, and a clinically significant result will be summarized separately for each absorbency arm using the subset of subjects in the Safety population who underwent gynecological examinations. Complete gynecological examination information will be listed.

9.6. Concomitant Medication

Medications will be coded using World Health Organization Drug Dictionary (WHO-DD) Enhanced B3 (September 2022).

All medication data will be listed. The listing will indicate whether the medication is considered a prior medication, concomitant medication, or both. Medications that started before first test article insertion date will be considered prior medications whether or not they were stopped before first test article insertion date. Any medications continuing or starting after first test article insertion date will be considered to be concomitant. If a medication starts before first test article insertion date and continues after first test article insertion date it will be considered both prior and concomitant.

9.7. Product Complaints

Information on product complaints that were not captured in the subject diaries or as adverse events will be provided in a separate listing.

10. Changes from Planned Analysis

Not applicable.

11. Other Planned Analysis

Not applicable.

13.1. Demographic Data Summary Tables and Figures

Table 2: Demographic Data Summary Tables and Figures

Table Number	Population	Table Title / Summary
Table 14.1.1	All subjects	Subject Disposition
Table 14.1.2	ITT	Demographics and Baseline Characteristics
Table 14.1.3	Safety	Exposure to Study Product

13.2. Validation Criteria Data

Table 3: Validation Criteria Data

Table Number	Population	Table Title / Summary
Table 14.2.1	MITT	Summary of Elongated Tampons
Table 14.2.2.1	Safety	Summary of Individual Tampon Entry Diary Responses
Table 14.2.2.2	Safety	Summary of Diary Responses Following Last Tampon Use
Table 14.2.3	ITT, Gynecological Exam Subset	Summary of Packaging and Labeling Interview Responses

13.3. Safety and Tolerability Data

Table 4: Safety and Tolerability Data

Table Number	Population	Table Title / Summary
14.3.1 Displays of Adverse Events		
Table 14.3.1.1	Safety	Overall Summary of Adverse Events
Table 14.3.1.2	Safety	Adverse Events by System Organ Class and Preferred Term
Table 14.3.1.3	Safety	Adverse Events by System Organ Class, Preferred Term, and Maximum Severity

Table Number	Population	Table Title / Summary
Table 14.3.1.4	Safety	Adverse Events by System Organ Class, Preferred Term, and Maximum Relationship to Study Product
Table 14.3.1.5	Safety	Adverse Events by System Organ Class, Preferred Term, and Maximum Frequency
14.3.2 Summary of Deaths, Other Serious and Significant Adverse Events		
Table 14.3.2.1	Safety	Serious Adverse Events by System Organ Class and Preferred Term
